### Comparators

Pharmacological treatment options for patients with schizophrenia who are nonresponsive to antipsychotic monotherapy will include (1) initiation of a second antipsychotic, (2) initiation of an antidepressant, (3) initiation of a mood stabilizer and (4) initiation of a benzodiazepine.

Within each clinical subgroup, treatment options may be refined by exclusions at the drug class or individual agent level. For example, antidepressants are generally not considered treatment alternatives in patients presenting with mania, but could reasonably be considered for patients in the remaining four schizophrenia subgroups: depression, anxiety, schizoaffective disorder, and uncomplicated schizophrenia. Unless it is not considered a reasonable treatment option for a specific subgroup, initiation of a new antipsychotic will serve as the reference category because it is a frequently recommended approach to improving treatment response and is a common treatment strategy across all of the clinical subgroups under study. A survey on the prescribing behaviors of clinicians who prescribe psychotropic medications for individuals with schizophrenia will inform these choices.

## Outcomes of interest

### Primary

The primary effectiveness outcome will be time to psychiatric hospitalization.

### Secondary

We will also investigate time to index treatment discontinuation, time to introduction of another psychotropic medication, psychiatric emergency department visits, all-cause hospitalization, and death.

We will investigate adverse effects of medications including incidence of major cardiovascular events and diabetes mellitus.

Outcomes	
Death	Date of death will be defined by the Social Security Death Master File.
Psychiatric Hospitalization	Hospital claims will define inpatient admissions with a first listed mental disorder diagnosis (ICD-9:290-310). High levels of agreement between diagnoses in inpatient medical records and inpatient claims have been reported for several mental disorder groups, including schizophrenia (100.0%), major mood disorders (98.7%), alcohol dependence (97.8%), and drug dependence (96.4%). 
Psychiatric ED Visits	Emergency department claims are a reliable source of diagnostic information in relation to medical records and a valid source of illness severity information.  Emergency department visits in which the first listed diagnosis is a mental disorder (ICD-9-CM: 290-319) will be defined as emergency department mental health visits.
Self-Injurious Behavior	Deliberate self-harm will be defined by an E-code of E950-E958, excluding late effects of deliberate self-harm (E959), on any inpatient, emergency department, or outpatient claim. High positive predictive values have been reported. 
Diabetes Mellitus	One or more claims with a physician diagnosis of diabetes will define diabetes mellitus. Using self-reported diabetes status as the criterion standard, $\geq 1$ physician claim with any diagnosis of diabetes or a diabetes complication (ICD-9 codes: 295.00-2950.93, 357.2, 362.0-362.02, 366.41) has acceptable sensitivity (68.5%) and specificity (96.9%), and (kappa=0.76).  Sensitivity of 90% and specificity of 93% with self-reported diabetes. 
Cardiovascular Events:	Acute myocardial infarction (AMI) (ICD-9-CM: 410) or stroke (430-438, except 435) will be defined by diagnostic codes on inpatient claims of $\geq 3$ days in duration.  With this AMI definition 75% met criteria for definite or probable AMI on independent review of cardiac biomarkers, electrocardiograms, presenting symptoms, and medical history, and an additional 12% had a suspected AMI. 

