### Data source and cohort identification

The data source will be national (45-state) Medicaid Analytic Extracts data (2001-2010). The cohort will consist of adults who are 18 to 64 years old and diagnosed with schizophrenia who initiate a new psychotropic medication after a period of stable antipsychotic treatment. Individuals who are 65 or older because will be excluded because they also have Medicare and receive pharmacy benefits through Medicare Part D.

Schizophrenia will be defined as  $\geq 2$  outpatient claims or  $\geq 1$  inpatient claim for schizophrenia [ICD-9-CM: 295] during 365 days of consecutive Medicaid enrollment immediately prior to the index date. Stable antipsychotic monotherapy will be defined by filled prescriptions for only one second-generation antipsychotic (excluding clozapine), and no other psychotropics, for  $\geq 90$  days immediately preceding the start of the index medication (t0). After the  $\geq 90$  days of stable treatment with a single second-generation antipsychotic, study patients will have had a change in therapy defined as (1) addition of a second antipsychotic or (2) addition of a different psychotropic drug class (antidepressant, mood stabilizer, or benzodiazepine). To ensure the patients are in active treatment there must be an active supply of antipsychotic medication on t0.

The eligibility criteria select a cohort of individuals that are likely to have schizophrenia, have received antipsychotic monotherapy prior to the index date, and are still experiencing problems for which a new psychotropic medication strategy was initiated. A 1-year period of eligibility prior to follow-up initiation ensures sufficient time to collect service use related covariates to characterize cohort members.

Patients with stable clozapine monotherapy will be excluded because clozapine is largely reserved for the most severely ill patients. Patients who implement more than one change in therapy at the index date (e.g., addition of a mood stabilizer and an antidepressant) will also be excluded.

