### *Propensity score estimation and application*

Propensity score methods involve two steps: estimation of the propensity scores and application of the propensity score. Estimation of the propensity scores involves decisions about which covariates to include in the prediction model of the propensity scores and what form the model should take. We will use expert opinion to select the variables to include in the propensity score. To estimate the propensity scores we will first use logistic regression including all baseline predictors occurring prior to treatment assignment. In addition, we will augment our analysis with another non-parametric method for building the propensity score model such as a generalized boosting algorithm implemented with regression trees. We will assess the sensitivity of our results to the choice of the propensity score model.

For the application of the propensity scores, we will use weighting by the odds to estimate the average treatment effect on the treated sample and weighting by the inverse probability of treatment weights to estimate the average treatment effect in the population.

We will examine the covariate balance using standardized differences in covariate means across the treatment groups after weighting, and address any significant imbalances.

**AIM 2 Heterogeneity of Treatment Effects:** Within the five subgroups, explore whether the comparative effectiveness and safety of alternative treatment strategies varies according to patient age and presence of a substance use disorder.

We will use similar Cox model techniques for the HTE analyses. First we will assess interaction of age and substance use variables with treatment. If such interactions are found, we will then perform analyses examining alternative treatment strategies stratified by age group or substance use.

The rationale for investigating patient age as a moderator of antipsychotic treatment effects follows from evidence that individuals early in the course of psychosis may respond differently to medications than people with more chronic illness. The rationale for investigating comorbid diagnosis of a substance use disorder as a moderator of treatment effects follows from evidence that people diagnosed with schizophrenia and comorbid substance use disorders respond more poorly to antipsychotic medications than those without comorbid substance use disorders.

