## Appendices:

### Appendix 1: Exclusion Diagnoses

### Appendix 2: Variables included in propensity scores

## Appendix 1: Exclusion Diagnoses (Contraindications for clozapine, other antipsychotics, or life threatening)

Diagnosis	ICD-9-CM Codes*
Narrow angle glaucoma	365.02
Myocarditis	422.x, 391.2x, 398.0x
Neutrophil disorders	288.00-288.04, 288.09, 288.1x
Malignant neoplasms	140-205
Epilepsy, seizure disorders	345.xx
Alzheimer's and other cerebral degenerations	331.xx

\* x indicates inclusion of any 5th digit if available for a diagnosis code.

xx indicates inclusion of any 4th and 5th digits if available for a diagnosis code.

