## Appendix 2: Variables included in the Propensity Score

### Demographics

---

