Other psychiatric medication	modafinil, oxybate, phendimetrazine, benzphetamine
OB/GYN medication	oral contraceptives, other contraception, medroxyprogesterone
Metabolic and related medication	lipid-lowering drugs, hypothyroid treatment, antithyroid agents, anorexiant
Cardiovascular medication	thiazide diuretic, ACE inhibitor/ARBs, other anti-hypertensives, other cardiovascular drugs
Respiratory/allergy medication	non-sedating antihistamines, other antihistamines, Corticosteroids, other Asthma medications, Smoking cessation
Gastrointestinal medication	histamine 2 receptor antagonists, proton-pump inhibitors, other prescription dyspepsia, Antacids, anti H pylori, phenothiazine antiemetics, Ulcerative colitis treatment
Neurologic/musculoskeletal medication	migraine treatment/prevention, NSAID, includes coxibs, narcotic analgesic, Non-narcotic analgesic (acetaminophen), Cyclobenzaprine, other skeletal muscle relaxants, other rheumatologic
Antibiotics	
Diabetic medication	
Hyperlipidemia medication	
Severe cardiovascular medication	

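### All-cause hospitalization counts delivery admissions, and pregnancy at t0 is neither an exclusion nor a propensity score variable: a small, assumption-dependent bias in one secondary outcome, easily removed

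*Combined protocol and SAP*

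**What the plan says.** The Secondary outcomes section lists "psychiatric emergency department visits, all-cause hospitalization, and death". The table that follows defines death, psychiatric hospitalization, psychiatric emergency visits, self-injury, diabetes and cardiovascular events. It has no row for all-cause hospitalization, and nothing elsewhere removes any kind of admission from it.

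The cohort section describes "adults who are 18 to 64 years old", and both sexes appear in Appendix 2. Appendix 1, headed "Contraindications for clozapine, other antipsychotics, or life threatening", lists glaucoma, myocarditis, neutrophil disorders, malignancy, epilepsy and cerebral degenerations, but not pregnancy.

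"Appendix 2: Variables included in the Propensity Score" has rows for gender, four-year age bands, Medicaid eligibility category and many diagnoses, among them appendicitis, cellulitis and diverticula. It has none for pregnancy, delivery or the puerperium. The nearest entry is a past-year drug class: "oral contraceptives, other contraception, medroxyprogesterone".

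Under Follow-up and censoring, the intent-to-treat window is 365 days, with censoring at loss of Medicaid. The section on confounding undertakes to control for a wide set of factors from the claims of the 365 days before initiation.

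**The concern.** A woman who is pregnant at t0, carries to term and stays enrolled will deliver inside a 365-day window, and a delivery in hospital is an event for this outcome. Pregnancy at t0 is therefore a strong baseline predictor of the outcome. Gender, age band, eligibility category and contraceptive fills indicate who could be pregnant, not who is, so weighting on them need not balance pregnancy between arms of the same age and sex mix.

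Two cases must be kept apart. If pregnancy also influences which of the four classes is started, the comparison is confounded: the class that pregnant women receive less often looks protective. If it does not, deliveries are spread evenly and only dilute the contrast. The stake is the all-cause hospitalization result, chiefly in uncomplicated schizophrenia, where the arms are large enough for a small bias to affect a significance test.

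**Working it through.** **The plan's own figures.** Under Sample size, 1,534 distinct patients per group (0.70 × 2,192) are said to give at least 80% power for a 5.0-point difference in one-year admission. No base rate is stated. A two-sided 0.05 test of two proportions gives power 0.913 for 20% vs 25%, 0.800 for 40% vs 45%, and a minimum of 0.791 near 50%. The figure reproduces, and nothing here disputes it. For uncomplicated and schizoaffective patients the plan cites a 4-point difference. At 6,967 per group (0.70 × 9,954, the smallest uncomplicated arm), power for 4 points is at least 0.997, so that subgroup can detect much smaller differences.

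**Inputs for the bias.** All are assumptions, because the documents give none of them:
- *f*, women aged 18–44 as a share of episodes: 20–30%
- share of them pregnant at t0: 2–4% in an arm that does not avoid pregnancy, 0.5–1% in one that does, so the difference *d* runs from 2 − 1 = 1.0 to 4 − 0.5 = 3.5 points
- *s*, share of those pregnant at t0 with a delivery admission observed in the window: 70–100%
- *b*, one-year admission risk from other causes: 35%

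**Spurious risk difference** = *f* × *d* × *s* × (1 − *b*)
- Low: 0.20 × 0.010 × 0.70 × 0.65 = 0.0009, about 0.1 points
- High: 0.30 × 0.035 × 1.00 × 0.65 = 0.0068, about 0.7 points

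**Detectable difference, uncomplicated schizophrenia** (80% power, two-sided 0.05, 70% of the Table 5 episodes) = 2.80 × √[0.35 × 0.65 × (1/n₁ + 1/n₀)]
- Antidepressant (0.70 × 25,061 = 17,543) vs second antipsychotic (0.70 × 27,005 = 18,904): 2.80 × 0.00500 = 1.4 points
- Mood stabilizer (6,968) vs second antipsychotic (18,904): 2.80 × 0.00668 = 1.9 points

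These are simple unweighted calculations. Weighting would widen them, and counting episodes rather than patients would narrow them.

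**Comparison**

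| | Low (0.09 points) | High (0.68 points) |
|---|---|---|
| Share of the 4-point benchmark | 2% | 17% |
| Share of 1.4 points (antidepressant) | 6% | 49% |
| Share of 1.9 points (mood stabilizer) | 5% | 36% |
| Chance of a significant result in the biased direction, no true effect (nominal 2.5%): antidepressant | 4% | 28% |
| Same, mood stabilizer | 3% | 17% |

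The last two rows are 1 − Φ(1.96 − bias/SE). For the high case, 0.00683/0.00500 = 1.36 and 0.00683/0.00668 = 1.02.

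**How far from 4 points?** With *b* = 35%, a spurious 4-point difference needs a whole-arm imbalance in pregnancy of 0.04/0.65 = 6.2 points (*s* = 100%) to 0.04/(0.65 × 0.70) = 8.8 points (*s* = 70%). The assumed inputs give whole-arm imbalances of only 0.20 × 1.0 = 0.2 to 0.30 × 3.5 = 1.05 points.

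**The case against.** The strongest objection is that the confounding step is undocumented. No section says that pregnancy affects the choice among a second antipsychotic, a mood stabilizer, an antidepressant and a benzodiazepine, and every number in the bias formula is assumed. This stands, and it is why the conclusion is conditional. The section on confounding does accept that physicians choose treatment on the clinical information they have. That makes the link plausible without establishing it.

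Second, the plan already covers part of the problem. Age and sex mix is balanced through the propensity score, the array analysis addresses unmeasured confounding in general, and variable choice is left open: "We will use expert opinion to select the variables to include in the propensity score". The 180-day and as-treated analyses would also capture fewer deliveries, as would the Aim 1 text, which censors at discontinuation or change of drug and so differs from the Follow-up section. These points reduce the concern but do not remove it. Imbalance within age and sex strata remains, the array analysis does not name pregnancy, and pregnancy can be read from the same claims.

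Third, counting every admission is what all-cause means, and dropping obstetric admissions would discard complications that might be related to treatment. This stands, and the outcome should not be redefined.

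Fourth, the power section already warns that large samples will make small differences significant and leaves their importance to stakeholders. That is fair for true differences, but it does not answer a difference produced by bias.

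A reader might infer more than the documents support. Pregnancy at t0 does not make an observed admission near certain: pregnancies may be lost, and follow-up ends at loss of Medicaid. Nor do the documents show that time to discontinuation is confounded. Conception after t0 is a post-baseline event, and a drug started in a woman known to be pregnant was started with that knowledge.

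**Conclusion.** The gap is real but minor. All-cause hospitalization includes deliveries as written, and pregnancy at t0 is neither excluded nor adjusted for. Whether this biases the comparison depends on prescribers weighing pregnancy when they choose among the classes, which is an assumption. Granting it, with the other inputs also assumed, the bias is about 0.1 to 0.7 points. It could not by itself produce a 4-point difference. In uncomplicated schizophrenia it could be about 5% to 49% of a detectable difference, depending on the comparison and the inputs. Without that assumption, the effect is only extra events unrelated to the strategies. The point is confined to one secondary outcome. The primary outcome requires a first-listed mental disorder code, so an admission coded first as a delivery is not an event there.

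**What to change.** - Add pregnancy at t0 to Appendix 2, defined for example as a pregnancy claim in the prior 9 months with no later delivery or termination claim. This lies within the 365-day baseline period and in the existing data.
- Give all-cause hospitalization a row in the outcome table, keep it as all admissions, and state that deliveries are included.
- Report a sensitivity analysis that omits admissions with a first-listed obstetric or delivery code, with the code list stated in advance.

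The cost is one covariate, one definition row and one extra analysis, with no new data source. The indicator will miss pregnancies with no claim by t0. Those not yet recognized could not have influenced the prescriber, so they add deliveries without confounding the choice.

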### Subgroups

From the base study population described above, 5 clinical subgroups will be defined based on the presence of psychiatric diagnoses during the 30 days prior to and inclusive of the treatment change under study (index date) and who have this same diagnostic code from more than one provider to increase the validity of the diagnostic groups. The subgroups will be defined by codes to capture 1) uncomplicated schizophrenia (with schizophrenia codes from at least 2 different providers and without any diagnoses that would qualify them for the other subgroups during the 365 days prior to the index date), 2) schizoaffective disorder (ICD-9: 295.7) as the most recent schizophrenia-spectrum diagnosis, 3) depressive (ICD-9: 293.83, 296.2, 296.3, 296.9, 298.0, 300.4, 311), 4) manic (296.0, 296.4-296.8), and 5) anxiety (293.84, 300.00-300.02, 300.09, 300.20-300.23, 300.29, 300.3, 300.7, 308.0-308.9, 309.21, 309.81, 312.39, 313.0, 313.21, 313.23). These subgroups are defined to reflect the reason for the change in treatment.

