#### AP treatment Initiation year

2002

2003

2004

2005

2006

2007

2008

2009

Diagnostic History, past year	ICD-9-CM Codes*
Depression	293.83, 296.2x, 296.3x, 296.9x, 298.0x, 300.4x, 311.xx
Anxiety	293.84, 300.0x, 300.2x, 300.3x, 308.3x, 309.21, 309.81, 313.0x, 313.2x, 313.89
Bipolar	296.xx (not 296.2x or 296.3x or 296.9x)
Substance use disorder	291.xx, 292.xx, 303.xx, 304.xx
Moderate/severe mental retardation	318.xx
HIV	042, 043, 044, 079.53, V08
Neoplasms	140.xx-239.xx (Exclude people with malignant neoplasms 140.xx-205.xx)
Diabetes	250.xx
Obesity	270.xx
Hyperlipidemia	272.0x-272.4x, 272.7x, 272.9x
White blood cell diseases	288.xx, 289.xx (exclude neutrophil d/o 288.00-288.04, 288.09, 288.1x)
Anemia	280.xx-285.xx
Drug-related dyskinesia	333.85
Hypertension	401.xx-405.xx
Ischemic heart disease	410.xx-414.xx
Pulmonary circulation diseases	415.xx-417.xx
Cardiac dysrhythmias	427.xx
Heart failure	428.xx
Cerebrovascular disease	430.xx-438.xx
Acute bronchitis and bronchiolitis	466.xx
Chronic bronchitis	491.xx
Pneumonia	480.xx-486.xx
Emphysema	492.xx
Asthma	493.xx
Appendicitis	540.xx-543.xx
Noninfectious enteritis and colitis	555.xx-558.xx
Diverticula of intestine	562.xx
Intestinal obstruction	560.xx
Chronic liver disease and cirrhosis	571.xx
Acute & chronic pancreatitis	577.0x, 577.1x
Cholelithiasis	574.xx
Acute kidney failure	584.xx
Chronic kidney failure	585.xx

Kidney infections	590.xx
Cellulitis and abscess	681.xx–682.xx
Osteoarthritis and allied disorders	715.xx
Intervertebral disc disorder	722.xx
Fractures, all sites	800.xx–829.xx
Fracture of neck of femur	820.xx
Poisoning by psychotropic medication	969.xx
Poisonings	960.xx–989.xx
Suicide and self-inflicted injury	E950-959
Intracranial injury	815.xx-854.xx
Severe cardiovascular diseases	401.0x-404.9x, 410.xx-416.xx, 425.xx-437.xx, 440.xx-447.xx
Schizophreniform	295.4x
Schizoaffective	295.7x

---

\* x indicates inclusion of any 5th digit if available for a diagnosis code.

xx indicates inclusion of any 4th and 5th digits if available for a diagnosis code.

Medication history, past year	Drug class
Psychotropic medication	
Antidepressants	SSRI/SNRI/mirtazapine, TCA and heterocyclic compounds, MAOI, trazodone-related antidepressants, bupropion
Mood Stabilizer	lithium, primary anticonvulsant, secondary anticonvulsant
ADHD medication	psychostimulants, alpha-agonists
Anxiolytic/hypnotics	benzodiazepines, GABA agonists, other newer or older anxiolytic/hypnotic

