**Health care services, past year**

- Mental Health Emergency Service
- Outpatient visits for Schizophrenia (0-9, 10-29, 30-49, ≥50)
- Hospital admissions for psychiatric illness (1, 2, 3, ≥4)
- Psychotherapy
- Psychosocial Service contacts

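### The primary outcome counts admissions first-listed ICD-9 290-310, but the adjacent ED outcome uses 290-319 for the same concept. As printed, an admission first-listed 311 is not a primary event.

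*Combined protocol and SAP*

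**What the plan says.** Under Outcomes of interest, Primary: "The primary effectiveness outcome will be time to psychiatric hospitalization". The codes for that event appear only in the outcome table printed under Secondary: "Hospital claims will define inpatient admissions with a first listed mental disorder diagnosis (ICD-9:290-310".

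The next row of the table, for psychiatric ED visits, counts visits whose "first listed diagnosis is a mental disorder (ICD-9-CM: 290-319".

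The Subgroups section uses codes above 310 for two of the five clinical subgroups. One is "depressive (ICD-9: 293.83, 296.2, 296.3, 296.9, 298.0, 300.4, 311". The other is the anxiety group, whose list ends "309.81, 312.39, 313.0, 313.21, 313.23".

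Appendix 2 (Diagnostic History, past year) again treats codes above 310 as psychiatric history. Its depression covariate is "293.83, 296.2x, 296.3x, 296.9x, 298.0x, 300.4x, 311.xx", and its anxiety list ends "309.21, 309.81, 313.0x, 313.2x, 313.89".

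Appendix 2 (Health care services, past year) includes "Hospital admissions for psychiatric illness" as a covariate but gives no codes for it, so it does not show which range is meant.

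**The concern.** Two adjacent rows apply the same rule, a first-listed mental disorder diagnosis, with different upper limits and no explanation. The narrower limit belongs to the primary outcome.

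Read as printed, a patient can enter the depressive subgroup on code 311 and then be admitted with 311 listed first without having a primary event. The same code on an ED claim would be a secondary event. Two programmers could also build different primary endpoints from this plan, one following the row literally and the other treating 310 as a misprint for 319.

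The planned sensitivity analyses would not expose the difference. They vary the follow-up length, the as-treated specification, the diagnostic subgroups and assumptions about unmeasured confounding. None varies the outcome code range.

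**Working it through.** **1. Which codes fall outside 290-310**

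The codes come from the Subgroups section and are compared by three-digit category with the two ranges in the outcome table.

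| Subgroup | Outside 290-310 | Outside 290-319 |
|---|---|---|
| Schizoaffective (295.7) | none | none |
| Depressive (7 entries) | 311 | none |
| Manic (296.0, 296.4-296.8) | none | none |
| Anxiety (14 entries as printed) | 312.39, 313.0, 313.21, 313.23 | none |

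The uncomplicated group is defined by schizophrenia codes (295), which are in range. The categories that count for ED visits but not for hospitalization are 311 to 319.

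**2. The plan's own power figure**

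The Sample size section claims at least 80% power to detect a 5.0-point difference in one-year admission with 1,534 patients per group. It states no base rate. For two proportions with pooled variance under the null and two-sided 0.05:

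power = Φ{ [d − 1.96·√(2p̄(1−p̄)/n)] / √([p1(1−p1) + p2(1−p2)]/n) }

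With n = 1,534 this gives 0.800 for 45% vs 40% and 0.791 for 52.5% vs 47.5%. The stated figure is therefore reproduced at rates near 50%, and power is higher at lower rates.

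**3. Illustration of lost events**

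The documents give neither the share of admissions first-listed 311-319 nor the admission rates, so both are assumed here. Suppose the same share s of events is lost in both arms. The 5.0-point difference becomes 5.0 × (1 − s):

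- s = 1%: 5.0 × 0.99 = 4.95 points
- s = 5%: 5.0 × 0.95 = 4.75 points

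Under that assumption these are lower bounds on the difference that remains, because a later in-range admission within 365 days still makes the patient a case.

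Worked example, 30% vs 25% with n = 1,534:

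- No loss: p̄ = 0.275, null standard error 0.01612, alternative standard error 0.01610. Then (0.05 − 1.96 × 0.01612)/0.01610 = 1.143, so power is 0.873.
- 5% loss: the rates become 28.5% and 23.75%, p̄ = 0.26125, and the standard errors are 0.01586 and 0.01584. Then (0.0475 − 1.96 × 0.01586)/0.01584 = 1.036, so power is 0.850.

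| Assumed rates | No loss | 1% lost | 5% lost |
|---|---|---|---|
| 20% vs 15% | 0.954 | 0.952 | 0.943 |
| 30% vs 25% | 0.873 | 0.869 | 0.850 |
| 52.5% vs 47.5% | 0.791 | 0.783 | 0.750 |

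The last row starts just below 0.80 because of its base rate. That shortfall has nothing to do with the code range.

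**4. Hazard ratio**

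Under proportional hazards, HR = ln(1 − p2)/ln(1 − p1).

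- No loss: ln(0.75)/ln(0.70) = 0.8066
- 5% loss: ln(0.7625)/ln(0.715) = 0.8083

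**The case against.** The strongest reply is that little depends on this. Every cohort member has schizophrenia claims (295), which are in range. So are all the schizoaffective and manic codes, six of the seven depressive codes and most of the anxiety codes. Any omitted admission is still counted under all-cause hospitalization, a secondary outcome. This argument stands as to size. It does not settle which admissions are primary events, and a secondary outcome does not restore a missing primary one.

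A second reply is that 310 may simply be a misprint. The same table prints diabetes codes as 295.00-2950.93, where Appendix 2 gives 250.xx, so it does contain code errors. That makes a slip more likely but does not prove one, and a misprint in the primary definition still has to be corrected.

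A third reply is that the ranges need not agree. Subgroup codes describe the 30 days up to the index date, and an inpatient outcome may properly have its own code list. The wider range would also bring in 318.xx, which Appendix 2 lists separately as moderate or severe intellectual disability. A narrower range could therefore be deliberate. The plan would then need to say so, and it does not.

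Finally, the equal-loss illustration leaves out the one mechanism that could bias a comparison, namely different use of 311 between arms. The documents contain no evidence for or against that.

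**Conclusion.** The concern holds. The primary outcome and the adjacent ED outcome give different ranges for the same concept. Exactly five subgroup-defining codes (311, 312.39, 313.0, 313.21 and 313.23) lie outside the primary range, and nothing elsewhere in the document resolves the difference. Code 311 is the clearest case: it defines the depressive subgroup and is listed as depression in Appendix 2.

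The effect is probably small. Its true size cannot be computed, because the documents give no admission counts by code and no admission rates. With assumed losses of 1% to 5%, equal in both arms, power falls by at most about 4 points in the cases shown, and in the one case worked (30% vs 25%, 5% lost) the hazard ratio barely moves. No bias between arms has been shown. The reason to act is that this row alone defines the primary event, so its meaning should not be left to the programmer. Whether 310 is a slip or a choice cannot be decided from the documents.

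**What to change.** Reconcile the two ranges before any outcome data are examined, in one of two ways:

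- Define psychiatric hospitalization by first-listed 290-319, to match the ED outcome, or at least add 311 and the four anxiety-subgroup codes to 290-310.
- If 290-310 is intended, state the reason and add a sensitivity analysis of the primary outcome using 290-319.

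The first costs one change of code range in the plan and the program. Its downside is that the full range admits some hospitalizations under codes such as 318.xx, which the ED definition already accepts; adding only the five codes avoids this. The second costs a sentence of justification and one extra run.
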